7.11.4. Exploratory Efficacy Endpoints

Exploratory efficacy endpoints include:

- Proportion of subjects in the ITT, MITT and PP Populations with a diagnosis of HABP >48 hours post-extubation up to, but not including, Day 22 in extubated subjects;
- Proportion of subjects in the ITT, MITT and PP Populations with development of VABP up to, but not including, Day 22;
- Incidence of all bacterial pneumonias up to, but not including, Day 22 in the MITT, ITT, and PP Populations;
- Incidence of other non-*S. aureus* pneumonias up to, but not including, Day 22 in the MITT, ITT, and PP Populations; and
- Incidence of other *S. aureus* infections acquired up to, but not including, Day 22 in the MITT, ITT, and PP Populations.
- Mechanical ventilation free days and ICU free days during the first 21 days, or prior to death, or early termination post randomization will be summarized descriptively and compared between treatment groups using a Wilcoxon rank sum test in the MITT, ITT, and PP Populations.
- Summary of pneumonia free days for subjects with *S. aureus* pneumonias, for subjects with bacterial pneumonias, and for subjects with any pneumonia in the MITT and PP Populations.
- Summary of All-cause mortality rate at Day 28 for subjects with any pneumonia in the MITT and PP Populations.

All exploratory efficacy endpoints will be descriptively summarized by treatment group.

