Semi-quantitative cultures using chromogenic media are preferred for determination of eligibility for randomization; however, any quantitative or semi-quantitative culture performed that indicates that a subject is heavily colonized with *S. aureus* is permitted if the culture results are available to randomize the subject within 48 hours (or up to 60 hours with Medical Monitor approval) from the time the ETA specimen was collected.

Once an enrolled subject has an ETA culture reported positive for heavy *S. aureus* colonization and meets all of the inclusion and none of the exclusion criteria, they are eligible for randomization. If they are not randomized on this occasion according to the protocol, they are no longer eligible for continued ETA sampling or randomization, and will be discontinued from the study; however, if subjects are extubated and subsequently re-intubated/mechanically ventilated, they are eligible for re-screening as a new subject enrollment, provided all entry criteria continue to be met. Subjects who were previously randomized are not eligible to be re-consented and re-screened.

At the time of randomization, if a subject's screening ETA culture also shows heavy colonization of a Gram-negative organism (i.e. heavy co-colonization of both Gram-positive and Gram-negative organisms), the subject will not be randomized into the study; however, randomization should not be delayed while waiting for Gram-negative results if heavy colonization with *S. aureus* has been confirmed. Testing for Gram-negative colonization is however not a requirement of the study protocol and would apply to centers that routinely test for both Gram-positive and Gram-negative organisms as part of standard of care.

Nasal swab specimens (one from each nostril) will be obtained at the Randomization Visit and will be cultured by the central microbiology laboratory. Results from the nasal swab specimen cultures will be used to assess correlation with results of the qualifying ETA culture.

Upon determination of eligibility, approximately 354 subjects will be randomized in a 1:1 ratio to 1 of 2 treatment groups:

- ASN100 administered as 2 separate intravenous (IV) infusions of ASN-1 and ASN-2 either sequentially or simultaneously, or
- Placebo administered as 2 separate IV infusions either sequentially or simultaneously.

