6. SAMPLE SIZE DETERMINATION

The estimated incidence of progression to *S. aureus* pneumonia in mechanically ventilated subjects with heavy endotracheal colonization of *S. aureus* is approximately 25% within 22 days of randomization.

Assuming a 2-sided significance level of 0.05 and a desired power of 80% to detect a significant difference between *S. aureus* pneumonia incidence rates of 25% in the placebo group and 12.5% in the ASN100 treatment group (50% reduction), 152 evaluable subjects are required in each treatment group. A sample size of 304 subjects (152 subjects per treatment group) will yield 80% power to detect a 50% reduction in the incidence of *S. aureus* pneumonia with ASN100 treatment when assuming a 25% incidence rate of *S. aureus* pneumonia in placebo-treated subjects. Assuming a 14% non-evaluable rate, approximately 354 subjects (177 subjects per treatment group) will be randomized. Assuming the screen failure rate is about 84%, approximately 2250 subjects will be screened.

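### Pneumonia-free days are summarised by arm only in subjects who developed pneumonia, so the table is not a randomized comparison and prevented cases drop out of it

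*SAP*

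**What the plan says.** SAP 7.11.4 lists, for the MITT and PP Populations, a "Summary of pneumonia free days for subjects with" S. aureus pneumonia, with bacterial pneumonia, and with any pneumonia. The section closes with "All exploratory efficacy endpoints will be descriptively summarized by treatment group", so the table is split by arm. Section 9 repeats the item among the analyses added to the protocol, but names two pneumonia groups instead of three. Neither place defines pneumonia-free days or says how death or early termination is counted.

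The next item in 7.11.4 is a "Summary of All-cause mortality rate at Day 28 for subjects with any pneumonia in the MITT and PP Populations". It sits beside SAP 7.11.3, where 28-day all-cause mortality in the full ITT, MITT and PP Populations is a secondary endpoint with Kaplan-Meier rates and 95% confidence intervals by arm.

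Other parts of the SAP use full denominators. Ventilator-free and ICU-free days, also in 7.11.4, are compared in the MITT, ITT and PP Populations. The primary analysis (7.11.1) divides events by all subjects in the arm.

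**The concern.** A count of pneumonia-free days in a prevention trial should credit a subject who never gets pneumonia with the whole window. Here that subject is absent. Membership of the summarised group is decided after randomization by the event the drug is meant to change, so the ASN100 cases and the placebo cases may differ for reasons other than treatment. What is left describes when the remaining pneumonias occurred, not how much pneumonia-free time each arm had.

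The by-arm columns could therefore show nothing for a drug that halves incidence, or could mislead in either direction, depending on which cases it prevents. At stake is the reading of one exploratory efficacy table in the study report, not the primary result.

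**Working it through.** **Inputs from the SAP.** Section 6 assumes S. aureus pneumonia in 25% of placebo and 12.5% of ASN100 subjects and states that "152 evaluable subjects are required in each treatment group". The efficacy window runs through Day 21.

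**The plan's own figure.** With pooled variance and no continuity correction,

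n = [1.960·√(2·0.1875·0.8125) + 0.842·√(0.25·0.75 + 0.125·0.875)]² / 0.125² ≈ 151.9, rounded up to 152 per arm.

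Allowing for 14% non-evaluable, 152/0.86 = 176.7, so 177 per arm and 354 in total. Both figures reproduce. The plan gives no figure for pneumonia-free days.

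**Who is left out.** Per 152 subjects, expected S. aureus cases are 152·0.25 = 38 on placebo and 152·0.125 = 19 on ASN100. The S. aureus row therefore omits 114 placebo and 133 ASN100 subjects.

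**Assumptions not in the documents.** Free days in a case = onset day minus 1. A subject without pneumonia scores 21. Placebo onset is uniform over Days 2 to 21. There are no deaths.

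**Case means.** Placebo cases have 1 to 20 free days, mean 10.5. ASN100 cases have:
- mean 10.5 if prevention is even;
- mean 5.5 if only the later half is prevented (remaining onsets Days 2 to 11, free days 1 to 10);
- mean 15.5 if only the earlier half is prevented (remaining onsets Days 12 to 21, free days 11 to 20).

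**All-subject means** = (1 − rate)·21 + rate·case mean.
- Placebo: 0.75·21 + 0.25·10.5 = 18.375.
- ASN100, even: 0.875·21 + 0.125·10.5 = 19.6875.
- ASN100, later half prevented: 0.875·21 + 0.125·5.5 = 19.0625.
- ASN100, earlier half prevented: 0.875·21 + 0.125·15.5 = 20.3125.

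| Cases prevented | Cases only: ASN100 vs placebo | Difference | All subjects: ASN100 vs placebo | Difference |
|---|---|---|---|---|
| Evenly | 10.5 vs 10.5 | 0 | 19.7 vs 18.4 | +1.3 |
| Later half only | 5.5 vs 10.5 | −5 | 19.1 vs 18.4 | +0.7 |
| Earlier half only | 15.5 vs 10.5 | +5 | 20.3 vs 18.4 | +1.9 |

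**A milder version.** The half-and-half patterns are extreme. Take onset uniform over Days 1 to 21 instead, so x = free days = 0 to 20 and the placebo case mean is 10.0. Let the chance that a case is not prevented fall linearly from 0.8 to 0.2 across the window (0.8 − 0.03x). The ASN100 case mean is (0.8·210 − 0.03·2870)/10.5 = 7.8, a cases-only difference of −2.2. The all-subject difference is (0.875·21 + 0.125·7.8) − (0.75·21 + 0.25·10) = 19.35 − 18.25 = +1.10. With the gradient reversed, the case mean is 12.2, the cases-only difference +2.2 and the all-subject difference 19.90 − 18.25 = +1.65.

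**Mortality in cases, as illustration.** Assume half of placebo cases are severe with 40% mortality, mild cases and non-cases have 20% mortality, and only mild cases are prevented. Mortality among cases is then 30% on placebo and 40% on ASN100. Overall mortality is 0.25·30 + 0.75·20 = 22.5% on placebo and 0.125·40 + 0.875·20 = 22.5% on ASN100.

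**The case against.** The other side has four arguments.

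- **Prevention is measured elsewhere with full denominators.** The primary analysis, the Kaplan-Meier analyses in SAP 7.11.2 and the incidence summaries in 7.11.4 all keep subjects without pneumonia. This stands, and no reader will have the cases-only table as sole evidence. But the Kaplan-Meier analyses cover S. aureus pneumonia and other S. aureus infection. For bacterial and any pneumonia, the cases-only table is the only timing measure planned.
- **The items are exploratory and descriptive.** This also stands. A Wilcoxon test is named for ventilator-free and ICU-free days and none for these summaries. It limits the weight of the point, but the table is still split by arm and its columns will be compared.
- **The term is undefined, so any bias is inferred.** The size does depend on my reading of it. Selection on the outcome does not: it follows from restricting the table to cases. If the wording was meant only to name the pneumonia type, it needs correcting before programming anyway.
- **The onset patterns are invented.** They are assumptions. Nothing in the documents suggests that late or mild cases would be prevented preferentially.

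A reader might also infer that 28-day mortality is reported only in subjects with pneumonia. It is not: SAP 7.11.3 gives it in the full populations, and the pneumonia-only table is an addition.

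**Conclusion.** The point holds for pneumonia-free days, as a limited, exploratory-level correction. The by-arm table conditions on the outcome under study and has no all-subject counterpart. At the design rates, a halving of S. aureus pneumonia gives a cases-only difference anywhere from −5 to +5 days across the three patterns, while the all-subject difference is positive in each (+0.7 to +1.9 days).

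These sizes rest on assumed onset, the onset-minus-one definition and no deaths. They apply to the S. aureus row only, because the plan gives no rates for bacterial or any pneumonia.

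One might infer that the table is biased against ASN100. The documents do not support a direction: if earlier cases are prevented, it flatters the drug. Nor do they support a claim that the trial would miss a working preventive, since the primary conclusion does not depend on this table. The pneumonia-only mortality table has the same selection problem but supplements a sound secondary endpoint.

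**What to change.** In SAP 7.11.4 and Section 9:

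1. Define pneumonia-free days through Day 21. Give subjects who survive without pneumonia the full 21 days, and state the rule for death and early termination before unblinding.
2. Summarise the measure by arm in all MITT and PP subjects for each pneumonia type. Add ITT, to match ventilator-free and ICU-free days.
3. Keep cases-only free-days tables, if wanted, as descriptions of cases, labelled as a non-randomized comparison.
4. Put the same label on the Day 28 mortality table in subjects with any pneumonia. It need not be replaced.
5. Make the pneumonia groups in the two sections agree (three in 7.11.4, two in Section 9).

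SAP Section 3 allows changes before unblinding. The cost is wording, reprogrammed free-days tables and a label on the mortality table. No new data are needed.

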7.11.5. Pharmacokinetic Endpoints

A listing of all PK serum sample collection dates and times and the PK BAL sample collection dates and times in the PK sub-study will be provided.

The statistical analyses for PK concentrations and parameters in serum and in BAL fluid in the PK sub-study will be performed by another vendor and described in a standalone PK analysis plan. The results will reside in a separate analytical report, which will be appended to the CSR.

7.12. Subgroup Analyses

The following subgroups will be used for subgroup analyses for the primary efficacy endpoint in the MITT and PP Populations, i.e. whether the subject has or doesn't have of *S. aureus* pneumonia up to, but not including, Day 22 for both SDO1 and SDO2

populations. The exploratory efficacy endpoints, the incidence of all pneumonias, and the incidence of other non-*S. aureus* pneumonias up to, but not including, Day 22 in the MITT and PP Populations, will also undergo the following subgroup analyses.

- Corrected Randomization stratification (Receipt or Non-Receipt of concomitant anti-staphylococcal antibiotics at the time of randomization that are potentially active against *S. aureus* pneumonia.)
- Type of ICU (e.g., SICU, MICU, Neuro ICU, Trauma ICU)
- Type of mechanical ventilation (Tracheotomy or Non-Tracheotomy) at Randomization
- Length of stay in the intensive care unit (ICU) post-treatment (<5, 5-12, >12-22, and >22 days)
- Duration of mechanical ventilation before randomization (48 vs. >48 hours)
- Baseline MRSA/MSSA from qualifying ETA culture
- Pneumonia MRSA/MSSA
- Reason for mechanical ventilation
- BMI categories: <25, 25-<30, 30-<35, and 35
- Age: <50, 50-<65, and >65
- WBC $\times 10^9/L$ at Baseline: <1, 1 to <2.5, 2.5 to <5, 5 to <10, and >10
- Platelet count $\times 10^9/L$ at Baseline: <50, 50 to <150; 150 to <400, and > 400
- Change in platelet count from Baseline: decrease by 50% or greater, or an increase by 50% or greater
- Male vs. female
- Smoker vs. non-smoker
- History of COPD vs. non-COPD
- History of alcohol use vs. no history of alcohol use
- Hospital readmission within 30 days after discharge
- Qualifying ETA and Screening ETA cultures: *S. aureus* only vs. co-colonized *S. aureus* and any Gram-negative at any time before randomization vs. co-colonized *S. aureus* and any other organism at any time before randomization
- Procalcitonin at Baseline for those who develop pneumonia vs. those who don't develop pneumonia: <median vs. median
- Qualifying ETA culture: *S. aureus* 3+ vs. 4+ vs. Heavy
- Cardiac events yes/no from receipt of study drug to Day 90 or early termination
- Multi organ failure yes/no from receipt of study drug to Day 90 or early termination

- Acute kidney injury defined by an absolute increase in serum creatinine of 0.3 mg/dL or a 50% increase (*viz.*, 0.3 mg/dL increase if baseline = 0.6 mg/dL and 50% increase if baseline is = 0.6 mg/dL) within 48 hours from receipt of study drug
- Presence of renal disease at Baseline: serum creatinine <2 mg/dL and = 2 mg/dl.

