7.8. Demographic and Baseline Characteristics

Demographic information including sex, race, ethnicity, corrected randomization stratification factor (receipt or non-receipt of concomitant anti-staphylococcal antibiotics at the time of randomization that are potentially active against *S. aureus* pneumonia), age (as a continuous variable and categorized as <55, 55 - <65, 65 - <75 and 75 years), height, weight, and BMI will be summarized by treatment group for the ITT, MITT, PP, PK, and Safety Populations.

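### As printed, the top subgroup bands in SAP 7.12 leave age 65, WBC 10 and platelets 400 in no band

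*SAP*

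**What the plan says.** SAP 7.12 introduces its list as follows: "The following subgroups will be used for subgroup analyses for the primary efficacy endpoint in the MITT and PP Populations", for both SDO1 and SDO2. The same subgroups apply to two exploratory endpoints, the incidence of all pneumonias and of other non-*S. aureus* pneumonias. Three entries in the list matter here:

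- age: "Age: <50, 50-<65, and >65"
- baseline WBC (×10⁹/L): "<1, 1 to <2.5, 2.5 to <5, 5 to <10, and >10"
- baseline platelets (×10⁹/L): "<50, 50 to <150; 150 to <400, and > 400"

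For the baseline table, SAP 7.8 has age "categorized as <55, 55 - <65, 65 - <75 and 75 years", which gives a 65-year-old a place. Protocol 4.1 admits adults from 18 with no upper limit, so age 65 is inside the eligible range.

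**The concern.** In each of the three variables the second-highest band excludes its upper limit, and the top band excludes the same value. A subject on that value has no row. For WBC and platelets this is one recorded value. For age it can be a whole year of life, because age is commonly stored in completed years.

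If the tables are programmed literally, the age, WBC and platelet rows can fall short of the MITT or PP total, and the oldest age group loses its youngest members. If a programmer repairs the bands without saying so, the output departs from the written plan, and the choice might be made after treatment codes are known.

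**Working it through.** **The plan's own figures.** The plan gives no figure for the number of subjects on a boundary value. Its sample size (SAP 6) is checked only to show that it does not depend on these bands. With rates of 25% and 12.5%, pooled rate 0.1875, two-sided alpha 0.05 and power 80%:

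n = [1.960 × √(2 × 0.1875 × 0.8125) + 0.842 × √(0.25 × 0.75 + 0.125 × 0.875)]² / 0.125² = (1.082 + 0.459)² / 0.015625 ≈ 152 per group.

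That makes 304 in total, and 304 / 0.86 ≈ 354 randomized, as the SAP states. No subgroup band enters this calculation.

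**Do the bands cover every value?** Each band was coded as printed, and a grid of values was tested for membership in exactly one band.

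| Variable | Grid | Values in no band, as printed | With an inclusive top band |
|---|---|---|---|
| Age | 18 to 110, whole years | 65 | none |
| WBC | 0.1 to 100.0, steps of 0.1 | 10.0 | none |
| Platelets | 1 to 1499, whole numbers | 400 | none |

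Every other value falls in exactly one band. The age bands of SAP 7.8, with the last read as 75 or older, leave no gap.

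**Could the extraction have dropped a sign?** In this SAP text, inclusive signs are often damaged. The BMI entry in the same list reads "BMI categories: <25, 25-<30, 30-<35, and 35", where the sign before the last number has gone. The last age band in 7.8 has lost its sign in the same way. Elsewhere the sign has become a superscript 3 (the fever threshold in 5.2.1) or, apparently, an equals sign (the baseline creatinine entry in 7.12). None of these examples has turned into a strict greater-than sign. The entry on ventilation before randomization shows the contrast on one line: a bare 48 is set against a strict greater-than 48 hours. The WBC and platelet entries, "5 to <10, and >10" and "150 to <400, and > 400", carry the strict sign explicitly, as does age. A lost sign is therefore unlikely, but the extracted text cannot exclude it.

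**How many subjects?** The documents give no age mean or SD, so the distributions below are assumptions. With age in completed years, the share lost is P(65 ≤ age < 66) = Φ((66 − m)/s) − Φ((65 − m)/s).

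| Assumed mean, SD | Φ at 66 − Φ at 65 | Share aged 65 | Of 304 | Of 354 | Share of those 65 or older |
|---|---|---|---|---|---|
| 50, 18 | 0.8130 − 0.7977 | 1.5% | 4.7 | 5.4 | 7.6% |
| 55, 17 | 0.7412 − 0.7218 | 1.9% | 5.9 | 6.9 | 7.0% |
| 60, 16 | 0.6462 − 0.6227 | 2.4% | 7.1 | 8.3 | 6.2% |
| 62, 15 | 0.6051 − 0.5793 | 2.6% | 7.9 | 9.2 | 6.1% |

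If age is computed as a fraction of years, only a subject at exactly 65.0 is lost. No count was worked out for WBC or platelets, since each gap is a single recorded value and the documents give no distribution.

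**The case against.** The strongest reply is that very little hangs on this. Section 7.12 attaches no test, multiplicity rule or decision to the subgroups, and nowhere says that its categories must cover everyone. The entry on change in platelet count names only falls and rises of at least 50% and leaves out those in between. A shortfall would show in the table denominators. SAP 8.2 provides for a separate programming specification, which may already settle the boundary, but that document is not available here. All of this stands, and it keeps the point minor. It does not supply the missing rule: the age, WBC and platelet entries are otherwise consecutive bands running from lowest to highest, and the written text omits one value from each.

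Three stronger readings are tempting, and the documents do not support them.

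- A reader might infer that every 65-year-old is certainly lost. That needs age in completed years, which the SAP does not state.
- A reader might treat the strict signs as proven original. The damage to inclusive signs in this text is not uniform, so the source file should be checked.
- A reader might conclude that the baseline age table and the age subgroups cannot be reconciled. Both schemes break at 65, so once 65 is assigned, the totals below 65 and from 65 upward can be compared directly. The differing lower cut-off (55 against 50) is a choice, and nothing requires the two sections to agree.

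**Conclusion.** The point holds as a minor wording error. As printed, 65, 10 and 400 fall in no subgroup band, and no other section assigns them. The age gap is the one that could be noticed: about 5 to 8 of 304 subjects, or 5 to 9 of 354, and roughly 6 to 8% of those aged 65 or older. Those counts rest on completed-year ages and on assumed normal distributions; with fractional age the loss is negligible. The conclusion also assumes that the printed signs match the source file, which is likely but not confirmed. The effect is confined to the subgroup tables for the primary endpoint and the two listed exploratory endpoints. The primary analysis, its error rate and the sample size do not change.

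**What to change.** Check the three signs against the source file. If they are as printed, amend SAP 7.12 so that the top bands read 65 or older, 10 or more, and 400 or more. With that change every tested value falls in exactly one band. It would help to state in the same sentence whether age is in completed years. Make the change before unblinding, which SAP 3 allows. The cost is a few words in the SAP and the matching lines in the table specification, with no effect on data collection or sample size. Aligning the remaining age cut-offs with 7.8 is optional and is not needed to correct the error.

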7.13. Analysis of Safety Data

All subjects in the Safety Population will be included in the safety analyses and analyzed based on the actual treatment received.

7.13.1. Adverse Events

Verbatim descriptions of Adverse Events (AEs) will be coded using Version 19.1 of MedDRA. Summary tables will be provided for all Treatment-Emergent Adverse Events (TEAEs). A TEAE is defined as an AE with a start date and time on or after the initiation of study drug administration. If the time of an AE is missing, it is considered treatment emergent if it starts on the same date as the initiation of study drug administration. All AEs (including non-TEAEs), Serious AEs (SAEs), and AEs leading to study drug discontinuation will be provided in listings by treatment group, subject ID, verbatim term, MedDRA system organ class (SOC) and preferred term (PT), start and end date, seriousness flag, severity, relationship to study drug, and action taken with study drug.

An overall summary of AEs will include the number and percentage of subjects in each treatment group who experienced at least one AE/TEAE in the following categories: any AE, any TEAE, any drug-related TEAE, any severe TEAE, any SAE, any drug-related SAE, any SAE leading to death, any TEAE leading to discontinuation of study drug, and any SAE leading to study drug discontinuation. Subjects with multiple events will be counted only once within each category. Severity grade and relationship will be counted using the maximum severity and the strongest relationship respectively for a subject with multiple TEAEs.

The number and percentage of subjects reporting a TEAE in each treatment group will be tabulated by SOC and PT; by SOC, PT, and severity; and by SOC, PT, and relationship (unrelated or related to study drug). For all analyses of TEAEs, if the same AE (based on PT) is reported for the same subject more than once, the AE is counted only once for that PT and at the highest severity and strongest relationship to study drug.

The number and percentage of subjects reporting a SAE and reporting a TEAE leading to discontinuation of study drug in each treatment group will be summarized by SOC and PT.

Listings will be provided for SAEs and AEs leading to drug discontinuation. In addition, all AEs will be listed.

